8.1 Primary Objectives

1. To describe the distribution of sensor collected data on physical activity, heart rate, heart rate variability, temperature, respiration rate, cough frequency, and sleep pattern, by severity of COPD exacerbations.
2. To predict moderate or severe COPD exacerbations by building a statistical model employing sensor-derived data and demographic and medical covariates.

8.2 Secondary Objectives

3. To evaluate the correlation of sensor collected data with
 - a) patients' self-assessed health status and symptoms (CAT) at baseline and study end,
 - b) lung function and lab values at baseline and study end,
 - c) and with history of mild, moderate and severe exacerbations at study end.
4. Sensor derived data may be related to the CAT score, therefore, an additional objective is to investigate whether changes in physical activity, heart rate, heart rate variability, temperature, respiration rate, cough frequency, and sleep pattern in the 3-month observation period, are associated with changes of the patient self-assessed symptoms (CAT).
5. To predict the CAT score and changes thereof by building a statistical model employing sensor-derived data and demographic and medical covariates.

CCI

A large black rectangular box covers the majority of the page below the 'CCI' text, indicating that the content has been redacted.

9 Research Methods

9.1 Study Design

9.1.1 Design Overview

This is a multicenter, prospective cohort study classified as “Sonstige Klinische Prüfung” (other clinical study) as per Art. 82 Regulation (EU) 2017/745 /§3 No. 4 MPDG. The study will be conducted at 11 sites in Germany, a cohort of participants with COPD stage II-IV will be followed for 3 months.

[figure not shown]
The device used in this study is a CE marked device modified to add a temperature measurement algorithm in addition to ECG and respiratory rate measurements (a modification solely regarding the software). This modification has not yet been evaluated by the Notified Body. The device will be utilized to collect physiologic data for analysis only. The data will not be communicated to the physicians or study participants during the study; therefore, this data cannot and will not be used to prevent, monitor, predict or diagnose disease or in any other way impact the treatment of the study participants. Data will be collected as close to the usual clinical practice as possible without applying burdensome or invasive procedures. The therapeutic strategy is not decided in advance

by the study protocol but will be determined as per normal clinical practice, and decision to prescribe a particular medication is fully independent from the decision to enroll the participant in the study. No medication or other therapeutic measure will be provided to the participants as part of the study.

A calibration cohort with non-COPD participants will be included and followed for 2 weeks.

See [Figure 1](#) for a graphical design overview.

Figure 1 Design Overview for COPD Cohort

Note: Exacerbation visit(s) could take place at any time point during the observation period, based on the occurrence of exacerbations.

COPD Cohort

Participants will be enrolled consecutively, in pulmonology practices and/or outpatient hospital settings during the regular scheduled clinical visits. The Baseline visit (Day 0) can take place once the participant provides written informed consent to participate in the study. Enrolled participants with COPD will be followed for a 3-month observation period.

During the Baseline visit each enrolled participant will be provided with a Vivalink wearable device and a connected phone and trained on the how to use these devices. The participants should wear the Vivalink device continuously, day and night (except for charging times and situations described in the instructions for use), during the observation period to ensure recording of ECG, accelerometer, and temperature data.

A study digital application is installed on the phone provided with the Vivalink wearable device for the participants to fill in the CAT questionnaire, label activities or events relevant for the interpretation of sensor signals, receive notifications/reminders and visualize their progress with study related activities.

The CAT questionnaire will be filled in by each participant at home, once per day, every day during the observation period electronically using the study digital application. The validated translation of the CAT questionnaire in German will be incorporated as an electronic questionnaire in the software application for the study participants. The participants will be trained during the baseline visit how to use the study application to fill in the CAT questionnaire.

The study digital application will be used also for the labeling of activities relevant for interpretation of data collected with the wearable device. The application will contain a predefined list of options: coughing, coughing with sputum production, spray use, non-scheduled spray use, eating, going to bed, waking up, walking, climbing stairs, and physical exercise that can be easily selected to indicate when such an event/activity occurs. The participants will be trained to use the application to correctly label events and activities. Participants will be requested to label at least 5 events per day, every day during the observation period.

The digital study application will also provide participants automated notifications/reminders related to the Vivalink device (e.g. to charge or to wear the device), to fill in the CAT questionnaire, and to input labeling information. Participants will be encouraged to fulfill these daily tasks by reminders and notifications triggered once data is not entered as requested. A dashboard with compliance data will be provided to the participants allowing them to have an overview of outstanding tasks and their performance to fill out questionnaires, wear the device, and label events to encourage them to be compliant.

A help line will be set up to assist participants in case of questions or issues regarding use of the Vivalink device or the digital application.

During the 3-month observation period the participants will attend visits at sites as per routine clinical practice in case of exacerbations, regular COPD check-ups, or other medical issues or events. At all visits at the study sites, assessments will be performed as per physician's judgement and documented as part of the routine clinical practice.

At the end of the 3-month observation period the participants will return the devices to the site during a regular COPD related visit scheduled at 3 months (\pm 14 days) after the baseline visit (Day 0). This will be the End of Study and assessments will be performed as per clinical practice.

In cases, when the End of Study does not align with an intended COPD related visit as per routine clinical practice, an End of Study visit will be scheduled at 3 months (\pm 14 days) after the baseline visit (Day 0) for the return of the devices. The assessments performed at this visit should be aligned with the clinical practice for a regular COPD related visit and costs shall be covered by the sponsor of the study.

In cases when the End of Study visit cannot be performed on site, the participants will be contacted via phone and provided with instructions to return the devices.

Death also defines End of Study. Although data from an End of Study visit will not be available, data from the patient will be used for analyses.

Calibration Participants Cohort

Participants will be enrolled in an internal medicine center in Germany. No additional procedures are required for establishing eligibility except for physician's judgement as described in the inclusion criteria (see [Section 9.2.1](#)). The Baseline visit (Day 0) can take place once the participants provided written consent to participate in the study. During the Baseline visit the enrolled participants will receive the following: the Vivalink wearable device (adhesive patch device with

ECG, accelerometer, temperature sensor), a connected phone, and training on how to use these devices.

The participants should wear the Vivalink device continuously, day and night, during a 2-week observation period in order to ensure recording of ECG, accelerometer and temperature data.

A study digital application is provided on the phone provided with the Vivalink device for the participants to label activities or events relevant for the interpretation of sensor signals and receive notifications/reminders. The application will contain a predefined list of options. The participants will be trained to use the application to correctly label as many such events as possible during the observation period.

At the end of the observation period, the participants will return the devices to the site. In case the participants are not able to visit the site, they will be provided with instructions on how to return the devices.

9.1.2 Outcomes

A complete mapping of objectives, outcomes and variables is available in Section [14.1.2](#).

9.1.2.1 Primary Outcomes

The primary objective is to 1) describe the distribution of sensor collected data with COPD exacerbations, as well as 2) to predict COPD exacerbations by building a statistical model.

Severity of acute exacerbations of COPD (AECOPD) are defined using the GOLD definitions based on treatment consequences (event-based) ([Vogelmeier 2017](#)): AECOPDs are defined as “an acute worsening of respiratory symptoms that results in additional therapy”. Exacerbations are classified as 1) **mild** if they are treated with short-acting bronchodilators only; 2) **moderate** if they are treated with short-acting bronchodilators plus antibiotics and/or oral corticosteroids; or 3) **severe** if the patient visits the emergency room or requires hospitalization because of an exacerbation.

The occurrence of exacerbations during the observation period will be defined as follows:

- For moderate/severe exacerbation requiring a physician’s intervention, emergency room visit or hospitalization, the severity, date of the exacerbation, and the duration of the exacerbation will be recorded via an eCRF.
- For mild exacerbations: self-reported; treated by the participant without intervention by a physician will be documented in the patient application labeling section (days with added treatment).

The duration of exacerbations during the observation period will be defined as follows:

The duration of a severe/ moderate exacerbation will be derived from the duration of added medication from the group of systemic corticosteroids and/or antibiotics which define moderate exacerbations by GOLD. Days in-hospital for severe exacerbations will also be captured.

The duration of mild exacerbations will be derived from the event “additional relieve medication taken” noted in the labelling section of the patient facing applicaton (which defines mild exacerbations). Duration and start / stop will be derived from these patient entries.

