		
Analysis, procalcitonin and CRP will be assessed as per standard practice at baseline (Day 0) and at study end (for details see Section 9.3)
 
c) number, date of onset and duration of mild, moderate, and severe exacerbations, respectively, during the observation period
	
 - Body plethysmography parameters: FEV1 [L], FVC [L], FEV1/FVC, TLC [L] (total lung capacity), RV [L] (residual volume), FRCpleth [L] (functional reserve capacity), IC [L] (inspiratory capacity), Raw [kPa s L-1] (=ratio of sRaw to FRCpleth; airway resistance), sRaw [kPa s] (specific airway resistance), VT [L] (mean tidal volume), ERV [L] (expiratory reserve volume), IRV [L] (inspiratory reserve volume). - Blood gas analysis:(capillary) pO2 [mmHg], O2 saturation [%] and pCO2 [mmHg] - Serum CRP [mg/l] and serum procalcitonin levels [ng/ml] - Blood count (CBC with differential); only values that are available with routine blood counts: Hb [g/dL], Hct [%], Erythrocyte count [$10^6/\mu\text{L}$], MCV [fL], MCH [pg], MCHC [pg/L], Reticulocytes [$\times 10^3/\mu\text{L}$] [% (of erythrocytes)], RDW [], platelet count [$10^3/\mu\text{L}$], WBC count [$\times 10^3/\mu\text{L}$], Lymphocytes [$\times 10^3/\mu\text{L}$] [%], Monocytes [$\times 10^3/\mu\text{L}$] [%], Neutrophils [$\times 10^3/\mu\text{L}$] [%], Eosinophils [$\times 10^3/\mu\text{L}$] [%], Basophils [$\times 10^3/\mu\text{L}$] [%] 
COPD exacerbations during the observation period from the physician charts (for the severe/moderate exacerbation) and from the patients app (for the mild exacerbations): Number, date of onset, duration of COPD exacerbations

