## 2.3 OUTCOME DEFINITIONS

### 2.3.1 Outcomes for primary objectives

The primary outcomes are based on COPD exacerbations. Exacerbations are classified as

- 1) mild if they are treated with short-acting bronchodilators only,
- 2) moderate if they are treated additionally with antibiotics or oral corticosteroids, or
- 3) severe if the patient visits the emergency room or requires hospitalization because of an exacerbation.

The occurrence of exacerbations during the observation period is measured as follows.:

- For moderate/severe exacerbation requiring a physician's intervention, exacerbation details will be recorded via eCRF by the clinical site. Severity, onset and duration will be derived according to the definition above from the documented COPD medication associated with the patients' exacerbation visit. The definition details for COPD medication and ATC codes will be finalized during the planned Data review meeting prior to the final analysis.
- For mild exacerbations: self-reported; treated by the participant without intervention by a physician will be documented in the patient application labeling section (days with added treatment: short-acting bronchodilators only). The start date and end date of addition of short-acting bronchodilators can thus be retrieved from the patient application. The documented use of additional medication (Bedarfsmedikament) will be considered as a mild exacerbation with the following rules for start and end days:
  - A mild exacerbation must start with at least 2 consecutive days of additional medication reported, the first day of consecutive medication will determine the start of the exacerbation.
  - If there are gaps in the additional medication reporting, a maximum of 2 days is allowed to be considered only one exacerbation. A minimum of 70% of the days must have additional medication reported. The end date of the exacerbation is the last day where both these rules are fulfilled.
- Any exacerbations that happen within 5 days will be considered as overlapping, as well as exacerbations that have an intersection in their start and end dates. Overlapping exacerbations will be considered as only one and classified as the graver one. (4)
  - If all overlapping exacerbations have the same type, the start date is the start date of the first exacerbation, and the end date of the last one.

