### 3.4.5 Analysis of outcomes

#### 3.4.5.1 Primary Objective 1

Descriptive statistics will be reported in terms of mean (SD) or median (IQR) for continuous variables, as well as counts and frequency (%) for categorical variables of sensor collected data described in section 2.1.4, comprised of

- physical activity,
- heart rate,
- resting heart rate,
- heart rate variability (10 variables),
- temperature,
- respiration rate,
- ratio of in- vs. expiration time
- cough frequency,
- sleep pattern (hours of sleep),
- frequency of additional medication

measured for each patient

1. at baseline (Day 0),
2. in the period Day 8 to Day 14 (intra-individual period average),
3. from 14 days prior to an exacerbation onset, in a 7-day sliding time window, in a 3-days sliding time window, and a 1-day sliding time window,
4. at the onset of an exacerbation (first day of exacerbation period),
5. from the end of an exacerbation to 14 days after, in a 7-day sliding time window, in a 3-days sliding time window, and a 1-day sliding time window,
6. 14, 21, and 28 days after an exacerbation.

The analysis will be repeated for different exacerbation severities:

1. Exacerbations of any (moderate or severe) severity are counted
2. Only severe exacerbations are counted
3. Only moderate exacerbations are counted
4. Only mild exacerbations are counted

Results will be reported in one table per parameter, with descriptive statistics indexing rows and measurement times indexing columns.

For each continuous parameter, mean values will be plotted across all daily measurement time points during the 3-month observation period, together with 95% CIs based on the normal approximation (t-statistic).

### 3.4.5.2 Primary Objective 2

To predict moderate or severe COPD exacerbations by building a statistical model employing sensor-derived data and demographic and medical covariates.

To generate several features needed as input to the model a number of algorithms (e.g., self-learning algorithms) for obtaining derived parameters such as cough frequency, physical activities and sleep pattern will be developed first using the label dataset obtained via the app (see Section 3.4.3).

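### Severe exacerbations are defined by ER visit or admission but timed by medication, so inpatient days beyond the drug course are tabulated as after the exacerbation

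*Protocol*

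**What the plan says.** Protocol 9.1.2.1 grades an exacerbation as severe "if the patient visits the emergency room or requires hospitalization because of an exacerbation". The grade carries no condition on steroids or antibiotics. For timing, the same section says that the duration of a severe or moderate "exacerbation will be derived from the duration of added medication from the group of systemic corticosteroids and/or antibiotics". It adds: "Days in-hospital for severe exacerbations will also be captured". Those days are given no part in the start, end or duration.

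The section also states, for moderate and severe events, that "the severity, date of the exacerbation, and the duration of the exacerbation will be recorded via an eCRF". The mapping table in Protocol 14.1.2 lists "Number, date of onset, duration of COPD exacerbations", with physician charts as the source for these events.

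SAP 2.3.1 repeats the three grades and says that the site enters exacerbation details in the eCRF. It then states: "Severity, onset and duration will be derived according to the definition above from the documented COPD medication", meaning medication linked to the exacerbation visit. The drug list and ATC codes are left to the data review meeting. ER and hospital dates are not named as a source.

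The resulting dates are used in four places:
- the Objective 1 windows in SAP 3.4.5.1, where the post-event windows run "from the end of an exacerbation to 14 days after" and a severe-only analysis is planned;
- the Objective 2 event, placed at onset (SAP 2.3.1);
- the days barred from control sampling, two weeks either side of the event (SAP 2.3.1);
- the merging of exacerbations within 5 days of each other (SAP 2.3.1).

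**The concern.** The criterion that makes an event severe and the data that time it are different things. A steroid or antibiotic course marks a moderate event. It need not start with the ER visit or admission, and it need not last until discharge.

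Two consequences follow. First, if a stay outlasts the course, the event ends on paper while the participant is still in hospital. Participants are asked to wear the patch day and night, so activity, sleep, heart rate and respiration from a hospital bed can be averaged into the columns for the period after the exacerbation. This matters most in the severe-only tables, where events are likely to be few. Second, the SAP gives no derived severity, onset or end for an ER or hospital event without qualifying medication, and it does not say that the eCRF entry then applies.

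**Working it through.** **1. The plan's own figure.** The plan gives no number for this definition. The nearest is the event count in Protocol 9.5, which this point does not contest. With 0.5 events per participant and a Poisson mean of 30, P(at least 18 events) = 0.993. Then 30 / 0.5 = 60 participants, and 60 / 0.9 = 66.7, rounded up to 67. These reproduce.

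**2. The rules side by side.**

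| Item for a severe event | Protocol 9.1.2.1 and 14.1.2 | SAP 2.3.1 |
|---|---|---|
| Severity | ER visit or admission; entered in eCRF | Same definition, but derived from COPD medication |
| Onset | Date in eCRF and charts | Derived from COPD medication |
| Duration or end | Entered in eCRF; derived from added steroid/antibiotic days | Derived from COPD medication |
| Hospital days | Captured, no role | Not mentioned |

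Medication records do not show whether someone attended an ER or was admitted, so the SAP's source cannot deliver the SAP's own definition of severe. For onset, the two documents name different sources and neither says which prevails.

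**3. Inpatient days counted as post-exacerbation.** The documents give neither stay nor course length, so the inputs are assumed: course and admission start on the same day.

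Inpatient days in the 14-day post window = max(0, min(14, stay − course)).

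| Course (days) | Stay 5 | Stay 7 | Stay 10 | Stay 14 |
|---|---|---|---|---|
| 5 | 0 | 2 | 5 | 9 |
| 7 | 0 | 0 | 3 | 7 |
| 10 | 0 | 0 | 0 | 4 |

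With a 5-day course, a 7-day stay puts 2/7 = 29% of the first post-event week in hospital, and a 10-day stay 5/7 = 71%. Whenever the stay is no longer than the course, the figure is 0.

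**4. Control days, for events with drug dates.** The zone after the end covers 14 days, so an inpatient day becomes eligible as a control only if stay − course exceeds 14. The largest surplus in the grid is 9, so none does.

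**5. Severe events without qualifying medication.** This step applies only if the SAP rule is followed strictly and the eCRF date is not used. If a share f of all expected events were unusable, the mean would be 30(1 − f):

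| f (assumed) | Mean | P(at least 18 usable events) |
|---|---|---|
| 0 | 30 | 0.993 |
| 5% | 28.5 | 0.986 |
| 10% | 27 | 0.973 |
| 20% | 24 | 0.913 |
| 30% | 21 | 0.773 |

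The documents give no value for f. In the severe-only tables, if 10% to 30% of the 30 expected events were severe (3 to 9), one lost event would be 1/9 = 11% to 1/3 = 33% of the data. For the controls, one undated event of an assumed 8 days would leave 14 + 8 + 14 = 36 days unprotected. Against about 60 × 90 = 5,400 person-days, that is 0.7%.

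**The case against.** The other side has real points. The duration sentence in the protocol concerns duration, not onset, and the protocol has a date and a duration entered in the eCRF. The SAP refers back to a definition that includes ER visits and hospitalization. It speaks of COPD medication more broadly than steroids and antibiotics, and it leaves the list open until data review. The protocol defines any exacerbation as worsening that leads to added therapy, so a severe event with no datable medication may be rare. A treatment-based duration is a deliberate choice in an exploratory study. The plan labels the windows only as following the exacerbation; it does not call them recovery.

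These points rule out three stronger readings that a reader might infer:
- *Both start and end come only from steroid or antibiotic dates.* This is not supported. The protocol records a date in the eCRF, and only the SAP takes onset from medication.
- *ER or hospital events without these drugs have no dates at all.* This is not supported. An eCRF date, a recorded duration and hospital days are all provided for. What is missing is a rule for using them.
- *Hospital days broadly contaminate the controls.* This is not supported. For events with drug dates the 14-day zone absorbs the surplus, and one undated event is a small share of person-days.

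The objection does not remove the core. The open drug list cannot help, because no list of drugs identifies an admission. And where the stay is longer than the course, the stated rule itself ends the event before discharge.

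**Conclusion.** The point holds as a mismatch between how severe events are defined and how they are timed, together with an unreconciled conflict between the SAP's derived dates and the protocol's eCRF entries. It is a stated rule that misplaces days, not merely missing detail.

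The certain effect is on the post-exacerbation columns of Objective 1, mainly severe-only, and only for stays longer than the drug course. Its size cannot be computed from the documents: the assumed grid gives 0 to 9 days per event. The effect on severe events without qualifying medication depends on how strictly the SAP sentence is applied and on a share that the documents do not give. The sample size of 67 is not called into question. The dates should be settled before the data review meeting.

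**What to change.** Amend Protocol 9.1.2.1 and SAP 2.3.1 as follows. This concerns the analysis definition only and does not touch treatment.

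- **Severity:** take the severe grade from the recorded ER visit or hospitalization, not from medication.
- **Start:** the earliest of the first day of added steroid or antibiotic, the ER visit and the admission.
- **End:** the latest of the last day of that medication and the discharge.
- **ER events without these drugs:** use the ER/eCRF date as onset and the eCRF-recorded duration for the end. Setting start and end both to the ER date would recreate the problem, because the next acute day would count as after the event.
- **Use:** apply these dates to the Objective 1 windows, the Objective 2 onset, the overlap rule and the control-day exclusion. State which source prevails when the eCRF and derived dates differ.

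The cost is a small change of wording and programming. Hospital days are already to be captured. Sites would need to enter the ER date if the eCRF does not hold it, and admission and discharge dates if hospital days are held only as a count. The eCRF duration must be a site entry, not a calculated course length, or it cannot serve events without these drugs.
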